12.3 Safety assessments

Safety and general tolerability of the investigational products will be based on TEAEs, physical examinations, including body weight, vital signs, ECGs and routine haematology, blood chemistry and urinalysis laboratory tests.

13 STATISTICAL METHODS

The data documented in this study and the parameters measured will be evaluated using classic descriptive statistics, i.e. geometric mean, geometric CV (%) (PK data only), arithmetic mean, SD, CV (%), minimum, median and maximum values for quantitative variables, and frequencies for qualitative variables.

Not available data will be evaluated as “missing values”. The statistical analysis of demographic and safety data will be performed using Statistical Analysis Software (SAS®) Version 9.3 or higher.

The pharmacokinetic parameters will be calculated using the actual recoded sampling times and non-compartmental methods with Phoenix WinNonlin (Version 6.3 or higher).

13.1 Analysis Sets

13.1.1 *Definitions*

A subject will be defined as screened after the signature of the informed consent, regardless of the completion of all the screening procedures.

A subject will be defined as eligible if he/she meets all the inclusion criteria and not meet any exclusion criteria. Otherwise he/she will be defined as a screen failure.

A subject will be defined as enrolled in the study if he/she is included into the interventional phase of the study. The enrolment will be performed through randomised allocation to a treatment cohort. An eligible but not enrolled subject will be defined as a reserve.

A subject will be defined as randomised in the study when he/she is assigned to a randomised treatment cohort.

The following analysis sets will be considered:

- Randomised set: all randomised subjects. This analysis set will be used for demographic, baseline and background characteristics.
- Safety set: all randomised subjects who receive at least one dose of the investigational medicinal product(s). This analysis set will be used for the safety analyses.
- PK set: all randomised subjects who fulfil the study protocol requirements in terms of investigational medicinal products intake and have evaluable PK data readouts, with no major deviations that may affect the PK results. This analysis set will be used for the PK analysis.

Each subject will be coded as valid or not valid for the Randomised set, Safety set and PK set. Subjects will be evaluated according to the treatment they actually receive.

13.1.2 *Reasons for exclusion from the PK set*

Reasons for the exclusion of subjects from the PK set are the following:

Before bioanalysis

- vomiting and diarrhoea after drug intake which could render the plasma concentration-time profile unreliable
- intake of concomitant medications which could render the plasma concentration-time profile unreliable
- AEs which could render the plasma concentration-time profile unreliable
- administration errors which could render the plasma concentration-time profile unreliable
- other events which could render the plasma concentration-time profile unreliable

If one of these events occurs, it will be noted in the CRF as the study is being conducted.

After bioanalysis

Exclusion of subjects on the basis of pharmacokinetic reasons is possible only for:

- subjects with non-zero baseline concentrations $> 5\%$ of C_{max} for single dose and first multiple dose (day 1 and day 8)

The samples from the subjects excluded from the PK set should still be assayed and the results listed. Subjects should not be excluded from the PK set if the AUC_{0-t} covers less than 80% of the $AUC_{0-\infty}$.

Any data excluded will be discussed in the CSR.

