4 INTRODUCTION

4.1 Safinamide

4.1.1 *Background*

The α -aminoamide derivative safinamide [(S)-(+)-2-[4-(3-fluorobenzyloxy) benzylamino] propanamide], developed as methane sulfonate salt, is an original anticonvulsant and antiparkinson agent which has been granted marketing authorisation in 9 EU Member States (i.e. Germany, Italy, Spain, Portugal, United Kingdom, Belgium, The Netherlands, Sweden and Denmark), in Norway and in Switzerland under the brand name of Xadago[®], 50 and 100 mg, film-coated tablets (2), for the treatment of adult patients with idiopathic Parkinson's disease (PD) as add-on therapy to a stable dose of Levodopa (L-dopa) alone or in combination with other PD medicinal product in mid-to late-stage fluctuating patients (3).

Safinamide uniquely combines potent, selective and reversible inhibition of monoamino oxidase B (MAO-B) with blockade of voltage-dependant Na^+ and Ca^{2+} channels and inhibition of glutamate release (4,8), thus showing a novel mode of action, targeting both dopaminergic and glutaminergic systems (9,10).

Data from Phase III clinical studies gave evidence that safinamide 50 or 100 mg/day improves the motor function in Parkinson's disease when prescribed as add-on therapy to dopamine agonists or L-dopa (3).

4.1.2 *Clinical pharmacology and pharmacokinetics*

Safinamide pharmacokinetics after single and multiple dose administrations have been described (11,12). At single ascending oral doses ranging from 2.5 to 10.0 mg/kg, safinamide was absorbed in a linear and dose-proportional fashion. Peak plasma levels were obtained on average at 1.8 to 2.8 h post-dose. Concentrations declined with a terminal half-life of 20 - 23h (11,12). Absolute bioavailability is high (95%), showing that safinamide is almost completely absorbed after oral administration and first pass metabolism is negligible (SmPC, 3). A complete long-lasting inhibition of platelet MAO-B activity was observed at all doses tested. Food intake prolonged the rate but did not affect the extent of safinamide absorption (11,12). Studies in healthy volunteers (13,15) demonstrated that safinamide does not affect oral tyramine metabolism mostly mediated by the intestinal MAO-A, and confirm that it can be administered without tyramine-related dietary restrictions.

4.1.3 *Safety*

The overall safety profile of Xadago[®] is based on the clinical development program performed on over 3000 subjects, of which over 600 were treated for more than 2 years.

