7.2 Discussion of design

Following a specific request of CFDA, the present study will be part of safinamide registration package in China and was designed according to CFDA guideline recommendations (1).

Safinamide has recently been granted marketing authorization in EU, Norway and Switzerland on the basis of the results of clinical trials performed in European countries. In the present study, safinamide pharmacokinetic profile, safety and tolerability after single dose and at steady state will be investigated for the first time in Chinese healthy male and female volunteers.

Two single doses (i.e. 50 and 100 mg) of safinamide will be administered to two subject¹ cohorts. The study will continue with multiple administrations of safinamide 50 and 100 mg, orally taken once a day for 7 days.

The 50 and 100 mg oral doses have been selected according to the common clinical practice (see Xadago[®] SmPC). These doses were investigated in the previously performed Phase III clinical trials. The volunteers will be assigned to the two cohorts according to the study randomised, parallel-group design.

Safinamide pharmacokinetic profile will be investigated after single dose, according to CFDA guidance requirements, and at steady state since multiple doses are administered in the clinical practice. Safinamide steady state should be reached after 5 or 6 days of treatment (day 13-14 in this study). Safinamide pre-dose concentrations will be assessed before the last 5 doses (days 10-14).

An open design was chosen. However, no bias on study outcome is expected considering that the study PK endpoints are based on the objective measurement of safinamide in plasma. Blood sampling time-points were selected on the basis of the known PK profile of safinamide. The sampling time lasts for about 4-7 elimination half-lives (mean PK half-life: 20-23 h) after both single dose and the last multiple dose administration.

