9.1 Study visits and procedures

Each study subject completing the study will undergo 8 visits plus a final visit.

The study protocol foresees 2 periods: in the first one the investigational products are administered in single dose, in the second one in multiple doses. The single dose in the first period and the first dose in the second period are separated by a wash-out interval of 7 days. Maximum and minimum study duration will be 32 and 20 days, respectively, screening visit included.

The first subject first visit (FSFV) is defined as the 1st visit performed at the clinical centre by the 1st screened subject. The last subject last visit (LSLV) is defined as the last visit performed at the clinical centre (or a telephonic follow-up, if applicable) by the last subject, i.e. the last visit foreseen by the study protocol, independently of the fact that the subject is a completer or a withdrawn subject.

The following phases, visits and procedures will be performed:

➤ Screening phase

- Screening – visit 1: between day -14 and day -2
- Period 1 – visit 2: day -1

➤ Interventional phase

- Period 1 – visit 3: days 1-3: single dose and blood sampling for PK analysis
- Period 1 – visit 4: days 4-5: blood sampling for PK analysis
- Wash-out interval of 7 days
- Period 2 – visit 5: days 8-9: first multiple dose and blood sampling for PK analysis
- Period 2 – visit 6: days 10-13: multiple doses and blood sampling for PK analysis
- Period 2 - visit 7: days 14-17: last multiple dose and blood sampling for PK analysis
- Period 2 - visit 8: day 18: blood sampling for PK analysis

➤ Final phase

- Final visit/early termination visit (ETV). In case of early discontinuation, discontinued subjects will undergo an early termination visit (ETV)

Study schedule

	Day	Procedures/Assessments	Notes
Screening – Visit 1	From day -14 to day -2	
 ➤ Explanation to the subject of study aims, procedures and possible risks ➤ Informed consent signature ➤ Subjects' screening number assignment ➤ Demographic data and lifestyle recording ➤ Medical/surgical history ➤ Previous/concomitant medications check ➤ Full physical examination (body weight, height, vital signs, physical abnormalities) ➤ ECG recording ➤ Clinical laboratory analyses: haematology, blood chemistry, urinalysis, serum virology and serum pregnancy test (women) ➤ Urine multi-drug kit test ➤ Adverse events check ➤ Inclusion/exclusion criteria evaluation ➤ Eligibility evaluation 	

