4.5.3 Pharmacokinetic Set

The PK Set will include all randomized subjects who fulfil the study protocol requirements in terms of IMP intake and have evaluable PK data readouts, with no major deviations that may affect the PK results. Any data excluded will be discussed at data review meeting before database lock. PK analyses will be based on the treatment cohort actually received, not on the treatment cohort to which the subject was randomized. The PK summaries and analyses will be based on the PK set.

Subjects may/will be excluded (depending on the protocol and IMP under study) from PK set if any of the following criteria are fulfilled:

Before statistical analysis

- Vomiting and diarrhea after drug intake which could render the plasma concentration-time profile unreliable.
- Intake of concomitant medications which could render the plasma concentration-time profile unreliable.
- AEs which could render the plasma concentration-time profile unreliable.
- Administration errors which could render the plasma concentration-time profile unreliable.
- Other events which could render the plasma concentration-time profile unreliable.

After bioanalysis

Subjects can be excluded from PK set only for the reason below:

- Subject with non-zero baseline concentrations $> 5\%$ of C_{max} for single dose and first multiple dose (day 1 and day 8).

The samples from the subjects excluded from the PK set should still be assayed and the results listed. Subjects should not be excluded from the PK set if the AUC_{0-t} covers less than 80% of the $AUC_{0-\infty}$.

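### The Day 8 limb of the 5% pre-dose rule can be met by slow elimination alone, and would then drop that subject's sound Day 1 and Day 14 profiles

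*Protocol*

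**What the plan says.** Protocol version 3.0, 13.1.2, lists several clinical and administrative reasons for leaving the PK set before bioanalysis, and a single reason afterwards: "Exclusion of subjects on the basis of pharmacokinetic reasons is possible only for" subjects whose non-zero baseline exceeds 5% of Cmax on Day 1 or Day 8. SAP version 2.0, 4.5.3, agrees: "Subjects can be excluded from PK set only for the reason below", followed by the same 5% limit "for single dose and first multiple dose (day 1 and day 8". The SAP does not settle whether exclusion is automatic: "Subjects may/will be excluded (depending on the protocol and IMP under study) from PK set" if a criterion is met.

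Three other provisions matter here.
- Protocol 13.1.1 codes each subject as valid or not valid for the PK set, and uses that set for the PK analysis. Nothing provides for validity by profile.
- Protocol 9.1 states that the single dose and the first dose of the second period "are separated by a wash-out interval of 7 days".
- Protocol 13.1.2 also requires excluded subjects' samples to be assayed and listed, exclusions to be discussed in the study report, and subjects to stay in the PK set even when AUC0-t covers less than 80% of AUC0-inf.

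**The concern.** A 5% limit is natural on Day 1, when no drug should be present. On Day 8 every subject has had the same dose 168 h earlier. If that dose was given correctly, pre-dose concentration over Cmax is governed by that subject's elimination half-life. Half-life and Kel are primary variables (Protocol 12.1.1), so the rule selects on something the study sets out to estimate, and any exclusion arising this way shifts the summaries in one direction.

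The per-subject coding enlarges the consequence. Residual drug on Day 8 cannot have affected the Day 1 half-life, Kel, CL/F or AUC0-inf, yet those values would leave the summaries too, together with the Day 14 profile.

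Protocol 7.2 says the PK profile "will be investigated for the first time in Chinese healthy male and female volunteers", so the 20-23 h figure comes from other populations. Reported half-life, exposure and spread are what a registration reader would use to judge whether Chinese subjects differ.

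**Working it through.** The plan gives no figure for Day 8 carry-over or expected exclusions, so there is nothing of its own to reproduce.

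**Inputs from the documents.** Dose interval 7 days = 168 h (Protocol 9.1). Mean terminal half-life 20-23 h and tmax 1.8-2.8 h (Protocol 4.1.2). Twelve subjects per cohort, 24 in total, no replacement (Protocol 13.2). **Assumed:** one-compartment oral kinetics, and lognormal half-life with CV 20-40%, because neither document gives a between-subject CV.

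**1. Ratio as a function of half-life.** With k = ln2/t1/2, and ka solved from tmax = ln(ka/k)/(ka-k), concentration is proportional to [ka/(ka-k)] x [exp(-kt) - exp(-ka t)]. The ratio is C(168) divided by the maximum over 0-24 h of C(t) + C(168+t). Dose, F and V cancel.

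| t1/2 (h) | Day 8 pre-dose / Day 8 Cmax |
|---|---|
| 20 | 0.32-0.33% |
| 23 | 0.67-0.70% |
| 30 | 2.1-2.2% |
| 35 | 3.6-3.7% |
| 39 | 5.0-5.1% |
| 45 | 7.2-7.4% |

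The ranges span tmax 1.8-2.8 h. The 5% line is crossed at 38.7-39.0 h. As a rough check, 2^(-168/39) = 5.0%. The threshold is 39/23 = 1.7 to 39/20 = 1.95 times the stated mean.

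**2. What the residual contaminates.** It makes up about 5% of Day 8 AUC0-24 at 39 h and 7-8% at 45 h. By Day 14 the Day 1 dose contributes 0.1-0.3% of AUC0-24. Its effect on the Day 1 profile is nil.

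**3. Chance of a breach.** With sigma = sqrt(ln(1+CV^2)), p = 1 - Phi[ln(38.9/median)/sigma], and the chance of at least one in 24 is 1-(1-p)^24. At a median of 21.5 h, ln(38.9/21.5) = 0.593.

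| CV | sigma | p | Expected in 24 | At least one in 24 |
|---|---|---|---|---|
| 20% | 0.198 | 0.14% | 0.03 | 3% |
| 30% | 0.294 | 2.2% | 0.5 | 41% |
| 40% | 0.385 | 6.2% | 1.5 | 78% |

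The expected shift in geometric mean half-life from removing everyone above the threshold is -0.1%, -1.5% and -4.9% respectively. At CV 30%, moving the median from 20 to 23 h gives 0.28-0.88 expected exclusions and a shift of -0.9 to -2.4%.

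**4. Effect of one exclusion in a cohort of 12.** Take one subject at 40-45 h through lower clearance, with the other 11 at 21.5 h. With volume fixed, AUC0-inf scales with half-life, so the geometric mean falls by 1-(21.5/40)^(1/12) = 5.0% to 1-(21.5/45)^(1/12) = 6.0%.

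**5. The same subject, excluded from Day 8 only.** The Day 1 results are then untouched. In the model that subject's Day 8 AUC0-24 is 1.23-1.29 times the others', so its geometric mean falls by 1-1.23^(-1/12) = 1.7% to 1-1.29^(-1/12) = 2.1%. The accumulation ratio is 2.67-2.82 against 1.86, so its geometric mean falls by 1-(1.86/2.67)^(1/12) = 3.0% to 1-(1.86/2.82)^(1/12) = 3.4%. Most of the avoidable effect therefore comes from excluding the whole subject.

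**The case against.** The strongest reply is that a breach is not expected. On the documents' own half-life the Day 8 baseline sits roughly 7-16 times below the limit, and with CV up to 30% fewer than one exclusion in 24 is expected. A distribution phase would raise Cmax relative to the tail and push the threshold above 39 h. The wording is permissive, and excluded data are listed and discussed, so a long half-life would not be hidden. The rule also has a proper purpose: above the threshold, carry-over is a visible part of Day 8 AUC0-24, the denominator of the accumulation ratio. All of this stands and limits the point to a conditional one. It does not justify discarding the Day 1 and Day 14 profiles. Listing does not repair the summary statistics, and the with-and-without analysis in SAP 4.4.2 is tied to major protocol deviations, which carry-over after correct dosing is not.

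Some stronger readings should be resisted.
- A reader might infer that the rule does remove low-clearance subjects and does bias the results. The documents establish neither. Exclusion is optional, and the trigger is half-life, which also depends on volume. If volume is the cause, CL/F and AUC0-inf need not shift.
- A reader might infer that the reported maximum half-life would collapse to about 21.5 h. That requires 11 identical half-lives. With CV 20-40%, the next-longest would typically be about 29-34 h.
- A reader might conclude that the Day 8 check should go. A high Day 8 baseline can also mean a swapped or mislabelled tube, a late pre-dose sample or unrecorded intake, and this is the only exclusion route left after bioanalysis.

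**Conclusion.** The point holds conditionally. The Day 8 limb can be met by slow elimination alone, at a half-life of about 39 h, and the per-subject PK set would then discard data that carry-over has not materially touched. The direction, toward shorter reported half-life, follows from the mechanism. The size depends on an unknown between-subject CV: negligible at 20%, about an even chance of mattering at 30%, likely to matter at 40%. If it happens to one lower-clearance subject in a cohort of 12, geometric mean AUC0-inf falls by about 5-6%. These figures rest on one-compartment kinetics, a lognormal half-life with median 21.5 h, and exclusion actually being exercised. It is worth correcting because the remedy is cheap and the present wording leaves the choice open until concentrations are known.

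**What to change.** Amend Protocol 13.1.2 and SAP 4.5.3 as follows.
- Keep whole-subject exclusion for a Day 1 pre-dose breach only.
- For a Day 8 breach, first look for a sampling, labelling or dosing error and document the outcome.
- If no error is found, keep the subject in the PK set for the Day 1 and Day 14 parameters. Flag the Day 8 parameters and the accumulation ratio, and report those with and without the flagged subject.
- As a sensitivity analysis only, give a Day 8 AUC0-24 with the residual removed, subtracting C_predose x exp(-Kel x t) with the subject's own Day 1 Kel.
- Replace the SAP's open wording on whether exclusion applies with this fixed rule.

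The cost is a change of wording, slightly more tabulation and one derivation from samples already scheduled. The drawback is that the corrected sensitivity values depend on the subject's Day 1 Kel, which is why the subtraction should not be the primary result.

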13.2 Sample size and power considerations

Twelve (12) healthy male and female Chinese volunteers / cohort (24 in total) will be included in the study in order to have at least 8 completers / cohort. Drop-out subjects will not be replaced. Since no hypothesis will be tested, no formal sample size calculation has been performed. The sample size of this study has been determined in agreement with the guidance issued by the Chinese Food and Drug Administration (CFDA) for clinical pharmacokinetic studies (1).

13.3 Demographic, baseline and background characteristics

Demographic and background characteristics will be examined according to qualitative or quantitative data. Qualitative data will be summarised in contingency tables. Quantitative data will be summarised using classic descriptive statistics. The baseline will be the last pre-dose measurement.

13.4 Analysis of pharmacokinetic parameters

A descriptive PK will be presented. The results will be displayed and summarised in tables and figures. Individual and mean curves (+SD at nominal times), indicating inter-subject variability, will be plotted. Data below the lower limit of quantification (BLQ) will be

considered as 0 in the calculations and presented as BLQ in listings and tables. As a consequence of BLQ (i.e. 0) values, calculated geometric means (if requested) could be null. For this reason, in the presence of any null value, the geometric mean will be reported as not calculated (NC).

13.5 Safety and tolerability evaluation

13.5.1 Adverse events

Adverse events (AEs) will be coded by System Organ Class (SOC) and Preferred Term (PT), using the Medical Dictionary for Regulatory Activities (MedDRA).

AEs will be classified as pre-treatment AEs (PTAEs) and treatment-emergent AEs (TEAEs), according to the period of occurrence, as follows:

- PTAEs: all AEs occurring before the first dose of investigational product and not worsening after the first dose of investigational product.
- TEAEs: all AEs occurring or worsening after the first dose of investigational product

Individual PTAEs and TEAEs will be listed in subject data listings. No summary table will be provided for PTAEs. TEAEs will be summarised by treatment and overall. The number and percentage of subjects with any TEAE and the number of TEAEs will be tabulated by SOC and PT, seriousness, relationship with investigational product and severity.

13.5.2 Physical examination

Date of the physical examination, overall investigator's interpretation (as normal or abnormal and, if abnormal, clinically significant or not clinically significant) and clinically significant abnormalities (if any) will be listed.

13.5.3 Laboratory data

Date/time of samples collection, overall investigator's interpretation (as normal or abnormal and, if abnormal, clinically significant or not clinically significant) and clinically significant findings (if any) will be listed. All laboratory results will be listed and a table of all the abnormal values will be presented.

13.5.4 Vital signs

Vital signs values will be listed and summarised by descriptive statistics.

13.5.5 Body weight

Body weight values will be listed and summarised by descriptive statistics.

13.5.6 ECG

Date/time of ECG recording, overall investigator's interpretation (as normal or abnormal and, if abnormal, clinically significant or not clinically significant) and clinically significant abnormalities (if any) will be listed. Hard copies of the ECGs will be attached as source document at site.

14 DEFINITION AND HANDLING OF AEs AND SAEs

